## Clinical Investigation Plan

## Title

*Confidential & Proprietary*

**Coil Assisted Flow Diversion: A prospective, single arm, multi-center study to assess the safety and performance of Neqstent in adjunctive therapy (CAFI Study)**

Follow-Up and Required Assessments	All implanted subjects will complete the scheduled follow-up assessments. Adverse events will be collected from device implantation through study duration. Table 2 highlights the required assessments:							
	Table 2. Schedule of Assessments							
		Baseline#	Procedure	Discharge	1-month (± 1 weeks)	6 months (± 1 month)	12 months (± 1 month)	24 months (± 1 month)
Medical history and medications		X					X	
Neurologic Exam		X		X	X	X	X	
NIH Stroke Scale		X	X*	X*	X*	X*	X	X*
Modified Rankin Scale (mRS)		X		X**	X**	X**	X**	X**
Medical history and medications		X					X	
Neurologic Exam		X		X	X	X	X	X
NIH Stroke Scale		X	X*	X*	X*	X*	X	X*
Modified Rankin Scale (mRS)		X		X**	X**	X**	X**	X**
Pregnancy test (pre-menopausal female)		X						
CT angiography (CTA) ^		X #				X	X****	
Magnetic Resonance Angiogram (MRA) ^		X #						
Cerebral Angiogram (DSA) ^		X # w/3D	X w/3D			X w/3D	X*** w/3D	
Adverse Event assessment			X	X	X	X	X	X
Procedure Information			X					
Aneurysm Occlusion Status – Raymond Roy and general assessment on study form ##			X			X	X***	

^ Baseline image aneurysm assessment can be made with either CTA, MRA **OR** DSA, upon MD discretion.  
# Baseline image screening can be completed within 3 months prior to enrollment. Imaging will always be performed on the day of the procedure which will be used for core laboratory baseline for comparison at 6 months.  
\* The NIH Stroke Scale score should be obtained within 24 hours after stroke in the event a subject is diagnosed with a stroke.  
\*\* mRS will be obtained at all scheduled visits.  
\*\*\* Cerebral angiogram is required at 6 months only; in the event of a Grade 2 or more using the Raymond Roy Scale at 6 months, a second cerebral angiogram assessment will be made at 12-month follow-up to re-assess for complete occlusion and will be reported as secondary efficacy.  

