## Clinical Investigation Plan

## Title

*Confidential & Proprietary*

**Coil Assisted Flow Diversion: A prospective, single arm, multi-center study to assess the safety and performance of Neqstent in adjunctive therapy (CAFI Study)**

Anticipated Risk	Percent Anticipated Risk Occurrence	Specified Risks
	Rarely (< 5%)	Intra-cranial hypertension
	Less Likely (5-15%)	Recanalization of the aneurysm
Vascular Access Site procedure related	Less Likely (5-15%)	Bleeding/Hematoma
	Very Rarely (< 3%)	Local infection
	Less Likely (5-15%)	Pseudoaneurysm
	Rarely (< 5%)	Thrombosis with resultant occlusion of access artery
	Rarely (< 5%)	Embolism with resultant occlusion of blood vessel
	Rarely (< 5%)	Arterio-venous fistula
Assessment (SoC) related procedure: Angiogram	Less Likely (5-15%)	
Allergic reaction to contrast media and Renal dysfunction secondary to contrast media.
 
Radiation exposure – the radiation dose of a cerebral angiogram is equivalent to about 2 years of background radiation and increases the risk of inducing cancer to 0.025% (1 in 4,000). Exposure of the fetus to radiation can harm the fetus and shall be avoided. In addition, if the subject is of child-bearing age, the doctor will ask the subject to undergo urine or blood pregnancy tests at the time of the procedure or angiograms to ensure that the subject is not pregnant.

Other Risks related to general anesthesia and medication therapy	Less Likely (5-15%)	Non-allergic drug reaction (local or systemic)
	Less Likely (5-15%)	Allergic drug reaction
	Rarely (< 5%)	Bleeding event – non-intracranial, non-access
	Rarely (< 5%)	Cardiovascular events
	Rarely (< 5%)	Peripheral vascular events
	Rarely (< 5%)	Gastrointestinal events

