- Distal embolization of particles or blood clot causing stroke
- Parent artery vasospasm
- Parent artery dissection
- Aneurysm recanalization
- Infection
- Device migration causing incomplete occlusion, hemorrhage or ischemic stroke

Contraindications:

- Allergy to platinum, nickel or titanium

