### 7.6.1 Angiogram

A cerebral angiogram that includes a 3D rotational angiogram shall be performed prior to the Neqstent implant placement procedure to allow proper assessment of the target IA being treated. The angiogram will include the acquisition of a 3D rotational angiogram of the aneurysm and parent vessel. Imaging will always be performed on the day of the procedure which will be used for core laboratory baseline for comparison at 6 months and at 12 months if performed due to lack of complete occlusion at 6 months. All imaging must be submitted to the independent core lab for analysis.

 Cerus Endovascular	Document Number DNQS428-01	Rev. F	Page 35 of 119
Clinical Investigation Plan	Title		
Confidential & Proprietary	Coil Assisted Flow Diversion: A prospective, single arm, multi-center study to assess the safety and performance of Neqstent in adjunctive therapy (CAFI Study)		

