## 7.9 Follow-Up

Following discharge, the subject will have a follow-up visit at 1 month, 6 months, 12 months and 24 months after the implant procedure. At each study visit, the subject shall be assessed for any new adverse events (AEs). A standard neurologic examination should be performed to evaluate for any new adverse events. A modified Rankin Scale (mRS) will be recorded at each follow-up visit. It is expected that most target IAs will be asymptomatic and the likelihood of post-placement neurologic changes is very low. The NIH Stroke Scale assessment should be obtained within 24 hour after a stroke in the event a subject is diagnosed with a stroke. Cerebral angiography will be repeated at 6 months and 12 months (if the Raymond Roy scale is Grade 2 or higher at 6 months). The cerebral angiography will include a 3D angiogram. The investigator should ensure that follow-up angiography is done with identical views to maximize the ability to compare baseline and post-treatment views. All angiographic images should be submitted to the independent core laboratory following the image transfer protocol. The target IA status shall be evaluated by an independent core laboratory.

The study's schedule of assessments and post-treatment visit windows are shown in

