**Table 8. Schedule of Assessments**

	Baseline #	Procedure	Discharge	1-month (± 1 weeks)	6 months (± 1 month)	12 months (± 1 month)	24 months (± 1 month)
Medical history and medications	X					X	
Neurologic Exam	X		X	X	X	X	X
NIH Stroke Scale	X	X*	X*	X*	X*	X	X*
Modified Rankin Scale (mRS)	X		X**	X**	X**	X**	X**
Pregnancy test (pre-menopausal female)	X						
CT angiography (CTA) ^	X #				X	X****	
Magnetic Resonance Angiogram (MRA) ^	X #						
Cerebral Angiogram (DSA) ^	X # w/3D	X w/3D			X w/3D	X*** w/3D	
Adverse Event assessment		X	X	X	X	X	X
Procedure Information		X					
Aneurysm Occlusion Status – Raymond Roy and general assessment on study form ##		X			X	X***	

^ Baseline image aneurysm assessment can be made with either CTA, MRA **OR** DSA, upon MD discretion.

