# Baseline image screening can be completed within 3 months prior to enrollment. Imaging will always be performed on the day of the procedure which will be used for core laboratory baseline for comparison at 6 months.

\* The NIH Stroke Scale score should be obtained within 24 hours after stroke in the event a subject is diagnosed with a stroke.

\*\* mRS will be obtained at all scheduled visits.

\*\*\* Cerebral angiogram is required at 6 months only; in the event of a Grade 2 or more using the Raymond Roy Scale at 6 months, a second cerebral angiogram assessment will be made at 12-month follow-up to re-assess for complete occlusion and will be reported as secondary efficacy.

\*\*\*\* CTA is required at 6 months only; in the event of a Grade 2 or more using the Raymond Roy Scale at 6 months, a second cerebral angiogram assessment will be made at 12-month follow-up to re-assess for complete occlusion and will be reported as secondary efficacy.

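### Aneurysm recanalization is a listed adverse event followed to 24 months, but subjects completely occluded at 6 months have no later scheduled imaging, so any late count is a lower bound

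*Combined protocol and SAP*

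**What the plan says.** **Recanalization as a safety event.** Table 5 in section 6.1 lists "Recanalization of the aneurysm" in the 5-15% band, without a time point. Section 6.1.1 repeats it ("Aneurysm recanalization") among the potential adverse events of the device.

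**Collection and analysis.** The Synopsis, under Follow-Up and Required Assessments, says: "Adverse events will be collected from device implantation through study duration". Table 8 has an adverse event assessment at every visit to 24 months. Section 10.6 takes all implanted patients as the safety population, tabulates adverse events by subject and by event, imputes nothing, and reports how many values were available for each analysis.

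**Imaging.** Section 7.9 states: "Cerebral angiography will be repeated at 6 months and 12 months (if the Raymond Roy scale is Grade 2 or higher at 6 months". Section 7.6.1 gives the same condition ("at 12 months if performed due to lack of complete occlusion at 6 months"), and so does the angiogram footnote to Table 8 ("Cerebral angiogram is required at 6 months only"). The CTA footnote follows the same rule. The 24-month column of Table 8 contains no imaging. A further footnote ties the Raymond Roy grade to an angiogram being done.

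**Clinical visits.** Section 7.9 adds: "It is expected that most target IAs will be asymptomatic and the likelihood of post-placement neurologic changes is very low".

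**12-month reading.** Section 10.1, the Table 8 footnotes and section 10.6 describe it as a re-assessment for complete occlusion. The Synopsis endpoints and section 10.4.1 add stability of the remnant. None names worsening.

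**The concern.** Recanalization is found by imaging. After month 6 the schedule images only subjects who were not completely occluded. Those who were completely occluded, and so had complete occlusion to lose, have clinical visits only, and the protocol itself expects those visits to show little neurologic change.

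Two readings of the final report are at risk. First, a low late recanalization count over all implanted subjects could be taken as a property of the device when it partly reflects who was imaged. The sentence in section 10.6 on reporting available data does not reveal this, because an event that nobody looked for does not appear as a missing value. Second, the 12-month reading re-examines 6-month failures only. If it is merged with the 6-month result, the merged rate can gain successes but cannot lose any.

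This matters because section 10.1 promises safety and performance information to 24 months, section 10 leaves assessment to clinical judgement on the data collected, and section 6.2 names better durability of embolization as a possible benefit.

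**Working it through.** **1. The schedule after month 6**

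| Status at 6 months | Imaging at 12 months | Imaging at 24 months | Other contact |
|---|---|---|---|
| Grade 1 | none scheduled | none | adverse events, neurologic exam and mRS at both visits; NIHSS at 12 months |
| Grade 2 or higher | angiogram | none | same |

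Section 7.7.3 mentions later comparisons at 6 and 12 months without the condition, but sections 7.6.1 and 7.9 and the footnotes to Table 8 all state it. A subject who first reaches Grade 1 at 12 months also has no later scheduled imaging.

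**2. The plan's sample size, reproduced**

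Inputs from section 10.6: 70% and 55% success, margin 10%, one-sided 5%, power 80%, attrition 10%.

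n = (1.645 + 0.842)² × (0.70 × 0.30 + 0.55 × 0.45) / (0.70 − 0.55 + 0.10)² = 6.18 × 0.4575 / 0.0625 = 45.3, rounded up to 46.

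46 × 1.1 = 50.6, rounded up to 51. Both stated figures are matched. (This is the per-arm formula of a two-arm non-inferiority design, which is a separate matter and does not affect this point.)

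**3. Subjects without later scheduled imaging**

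Assumption A: the 70% (or 55%) is the Grade 1 rate at 6 months. Section 10.6 ties the sample size to a composite of the primary endpoint components, so the plan does not say this.

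- At 70%: 46 × 0.70 = 32.2, about 32 not re-imaged by schedule and about 14 re-imaged.
- At 55%: 46 × 0.55 = 25.3, about 25 and about 21.

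**4. Losses without scheduled detection**

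Assumption B: the 5-15% band of Table 5 applies after 6 months, although it carries no time point.

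| Loss rate after 6 months | Among 32.2 Grade 1 | Among 25.3 Grade 1 |
|---|---|---|
| 5% | 1.6 | 1.3 |
| 15% | 4.8 | 3.8 |

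If only half of the band fell after 6 months (2.5% to 7.5%), the figures for 32.2 subjects are 0.8 to 2.4.

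For illustration only: section 4 cites a 45-patient series of another intrasaccular device in which complete occlusion went from 30 patients at a median of 6 months to 26 at a median of 13 months. The net loss is 4/30 = 13.3% (exact 95% interval 3.8% to 30.7%), and 32.2 × 0.133 = 4.3. A different device and a small series make this a rough guide.

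**5. Direction of a combined 6-or-12-month rate**

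Take 32 of 46 Grade 1 at 6 months (69.6%) and suppose that 3 of the 14 others convert by 12 months.

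- Combined rate as it would be reported: (32 + 3)/46 = 76.1%.
- Rate at 12 months if 1.6 of the 32 had lost Grade 1: (35 − 1.6)/46 = 72.6%; if 4.8 had: (35 − 4.8)/46 = 65.7%.

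The combined figure is the same in both cases, because no scheduled reading can subtract from it. Within the re-imaged group, 3/14 = 21.4% with an exact 95% interval of 4.7% to 50.8%.

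**The case against.** The strongest reply is that no recanalization analysis is planned. Section 10.6 promises generic adverse event tables, with no recanalization rate, no interval and no comparison with Table 5, and the study is descriptive and unpowered. That is right as far as it goes. Even so, a listed adverse event assessed at every visit will enter those tables, and nothing limits its count to 6 months or to imaged subjects.

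Several stronger readings are tempting, and the documents do not support them:

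- A reader might infer that late recanalization cannot be seen at all. Unscheduled imaging is not prohibited and symptomatic events would be reported, so detection is incomplete, not absent. Loss before 6 months shows in the 6-month grade, and worsening of a Grade 2 or higher remnant can be seen at 12 months.
- A reader might set a zero count among 51 implanted subjects, with its confidence limit, against an expected late loss rate. The plan makes no such comparison, and it would set all subjects over the whole period against Grade 1 subjects after 6 months.
- A reader might argue that the sponsor loses a signal for suspension. Section 12.2.15 sets no threshold for a high rate of known events, and enrolment is expected to last 6 months, so a signal arising after 6 months would come about when enrolment closes or later.
- A reader might want a late rate among Grade 1 subjects who happened to be imaged. Such imaging may be prompted by symptoms, so that rate would itself be biased.

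The case report forms are not reproduced, so how unscheduled imaging is recorded cannot be checked.

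**Conclusion.** The concern holds as one of incomplete ascertainment. Late loss of complete occlusion has no scheduled detection in subjects who are Grade 1 at 6 months, nor in those who first reach Grade 1 at 12 months. Any recanalization count after 6 months is therefore a lower bound, and the plan's missing-data reporting does not show this.

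On assumption A about 32 of 46 subjects are affected (about 25 at 55%). With assumption B as well, about 1.6 to 4.8 losses among the 32 would have no scheduled detection. Both assumptions go beyond what the plan states, so these figures indicate scale only. A combined 6-or-12-month occlusion rate can only move upward. The 6-month primary performance result is unaffected, and no error rate is at issue.

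A related inconsistency should be settled at the same time. The Synopsis (Study Size and Duration) and section 11.5 call the conditional 12-month visit follow-up for the primary endpoint, whereas the Synopsis endpoints and sections 10.4.1 and 10.6 set primary performance at 6 months and treat the 12-month reading as secondary.

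**What to change.** In section 10.6, under Endpoint Analysis:

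- Report recanalization separately up to and after the 6-month angiogram.
- For the first period, keep all implanted subjects as the base and state how many had a gradable angiogram.
- For the second period, give by 6-month grade the number imaged (scheduled or unscheduled) and the number not assessed. List events found in Grade 1 subjects as counts without a rate, and do not count Grade 1 subjects who were not imaged as event-free.
- Report the 12-month secondary endpoint only among subjects graded 2 or higher at 6 months, as conversion, stability or worsening, with that denominator and an exact interval.
- Present no combined 6-or-12-month figure as evidence of durability.

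In the Synopsis (Study Size and Duration) and section 11.5, reconcile the description of the 12-month visit with the 6-month primary performance endpoint.

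The cost is one paragraph, two table shells and one sentence in each of the two places. Visits, imaging and sample size stay as they are; whether later imaging is warranted is for the sponsor, and none is proposed here. The downside is that, if the success rate is near the planned figures, the report must say openly that most 6-month successes were not systematically assessed for late recanalization.

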**Table 8.**

 Cerus Endovascular	Document Number DNQS428-01	Rev. F	Page 37 of 119
Clinical Investigation Plan	Title		
Confidential & Proprietary	Coil Assisted Flow Diversion: A prospective, single arm, multi-center study to assess the safety and performance of Neqstent in adjunctive therapy (CAFI Study)		

**Table 8. Schedule of Assessments**

	Baseline #	Procedure	Discharge	1-month (± 1 weeks)	6 months (± 1 month)	12 months (± 1 month)	24 months (± 1 month)
Medical history and medications	X					X	
Neurologic Exam	X		X	X	X	X	X
NIH Stroke Scale	X	X*	X*	X*	X*	X	X*
Modified Rankin Scale (mRS)	X		X**	X**	X**	X**	X**
Pregnancy test (pre-menopausal female)	X						
CT angiography (CTA) ^	X #				X	X****	
Magnetic Resonance Angiogram (MRA) ^	X #						
Cerebral Angiogram (DSA) ^	X # w/3D	X w/3D			X w/3D	X*** w/3D	
Adverse Event assessment		X	X	X	X	X	X
Procedure Information		X					
Aneurysm Occlusion Status – Raymond Roy and general assessment on study form ##		X			X	X***	

^ Baseline image aneurysm assessment can be made with either CTA, MRA **OR** DSA, upon MD discretion.

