**Table 6. Eligibility Criteria**

Inclusion Criteria	Exclusion Criteria

Patients of all genders who meet all indications and contraindications will proceed to implantation.
 
 
1. Patient's indication for treatment of unruptured IA according to the national/international guidelines.
 
2. Age 18-80 years at screening
 
3. Patients who are suitable for non-emergency endovascular embolization of saccular IAs
 
4. IA located at a bifurcation in the anterior or posterior circulation with dimensions consistent with implant size selection guidelines included in the IFU
 
5. Patient has the necessary mental capacity to participate and is willing and able to participate in the study for the duration of the study follow-up and is able to comply with study requirements
 
6. Patient able to give their informed consent can be included in this study. This must be demonstrated by means of a personally signed and dated informed consent document indicating that the subject has been informed of and understood all pertinent aspects of the study.
 
	
The presence of condition that may create unacceptable risk during the aneurysm embolization procedure, such as patients with:
 
 
1. Ruptured aneurysm
 
2. Patient anatomy or physiology considered unsuitable for endovascular treatment
 
3. Any patient anatomy, physiology, existing implants with failed aneurysm embolization that would interfere with the ability for Neqstent to seal at the neck of the aneurysm. (i.e., compacted coils in close proximity to the neck that prevent good apposition of the Neqstent to the wall of the aneurysm, stent and/or stent-like devices whose struts span the aneurysm neck to retain the coil mass that inhibit access and/or successful Neqstent seating at the aneurysm neck, and/or any aneurysm that has a failed device and confirmed thrombus-burden inside the aneurysm sac)
 
4. Contraindication for arterial access
 
5. Largest measured IA neck diameter >8 mm or <3 mm
 
6. Target IA contains other devices/implants (e.g., coils) that will prevent complete expansion of Neqstent
 
7. Known allergy to platinum, nickel or titanium
 
8. Known allergy to contrast agents
 
9. Contraindication to anticoagulants or platelet inhibitor medication
 
10. Stenosis of the target IA's parent vessel >50%
 
11. Anticoagulation medications such as warfarin that cannot be discontinued.
 
12. Pregnant, breastfeeding or women of childbearing potential not on adequate birth control (only women with a highly effective method of contraception [oral contraception or intra-uterine device] or sterile women can be enrolled to the study)
 
13. Acute / chronic renal failure (including dialysis); Creatinine > 2.00 mg/dL or > 182 µmol/L
 
14. Myocardial Infarction, Stroke or TIA within the last 6 months
 
15. Any other medical issue within the brain that precludes the device implantation such as brain surgery, radiation in the target area of intervention, acute traumatic craniocerebral injury, etc.
 
16. Other medical conditions that cause an inability to comply with study requirements and/or that could increase the risk of neurovascular procedures or death within 2 years (e.g., liver failure, cancer, heart failure, chronic obstructive pulmonary disease, immunosuppression, neural disease, and hematologic disorders etc.)
 
17. Participating in another study with investigational devices or drugs that would confound the effects of the study outcomes
 
18. The presence of condition that may create unacceptable risk during the aneurysm embolization procedure
 

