### 12.1.6 Compliance with CIP

The PI is responsible for ensuring that his/her site complies with the CIP. The PI will:

- maintain oversight of the study at the clinical site
- sign an investigator agreement form
- conduct the investigation in compliance with this CIP, applicable sections of ISO 14155:2011, and requirements of the EC to ensure the safety and well-being of study subjects
- create, maintain and make available source documents for study subjects
- not implement any change to the CIP without prior approval from the sponsor, local EC, and (if required) regulatory bodies if required
- not deviate from the CIP, except to maintain the subject's rights, protect the life and physical well-being of a subject in an emergency, or the scientific integrity of the investigation
- document all deviations from the CIP
- ensure that the site has adequate staff and capabilities
- ensure that site equipment used in the study is maintained and calibrated
- ensure the accuracy, completeness and timeliness of study data in CRFs and reports
- allow and support sponsor monitoring and auditing activities
- be available to monitors and the sponsor to address questions during study visits
- be available and support regulatory authorities during audits
- respond in a timely manner to sponsor inquiries
- make reasonable efforts to prevent early withdrawal
- make reasonable efforts to ascertain the reason for early withdrawal

 The sponsor may also document deviations from the CIP

 Cerus Endovascular	Document Number DNQS428-01	Rev. F	Page 50 of 119
Clinical Investigation Plan	Title		
Confidential & Proprietary	Coil Assisted Flow Diversion: A prospective, single arm, multi-center study to assess the safety and performance of Neqstent in adjunctive therapy (CAFI Study)		

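### The schedule of assessments marks the pregnancy test at Baseline only, although Table 5 commits to testing at angiograms and DSA and CTA are due at 6 months and, for some subjects, at 12 months

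*Combined protocol and SAP*

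**What the plan says.** **The commitment.** The angiogram row of Table 5 (Section 6.1, Potential Risks) states the hazard: "Exposure of the fetus to radiation can harm the fetus and shall be avoided". For a subject of child-bearing age it goes on: "the doctor will ask the subject to undergo urine or blood pregnancy tests at the time of the procedure or angiograms".

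**The schedule.** Table 2 (Synopsis) and Table 8 (Section 7.9) both contain the row "Pregnancy test (pre-menopausal female)". In each table it is marked in the Baseline column only. The Procedure, Discharge, 1-, 6-, 12- and 24-month columns are blank, and the row carries no footnote.

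**The imaging.** Section 7.9 says: "Cerebral angiography will be repeated at 6 months and 12 months (if the Raymond Roy scale is Grade 2 or higher at 6 months"). The tables also mark CTA at 6 months, with a conditional mark at 12 months. The CTA footnote begins "CTA is required at 6 months only" and then calls for a second angiographic assessment at 12 months in subjects who are not Grade 1.

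**The entry safeguard.** Exclusion 12 (Table 6) limits enrollment of women of childbearing potential: "only women with a highly effective method of contraception [oral contraception or intra-uterine device] or sterile women can be enrolled to the study".

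**The concern.** Table 5 is a risk table. Section 7.9 points to Table 8 as the schedule of assessments, and that is the table a site can be expected to build its visit checklists from. A site could complete every assessment marked there and still perform DSA and CTA on a pre-menopausal woman whose last scheduled test was before the implant, months earlier.

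What is at stake is the safety of a fetus in an unrecognised pregnancy, which the plan itself says must be protected from radiation. No endpoint, sample size, power or error rate is involved.

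**Working it through.** The main check compares text with the schedule; the plan gives no figure to reproduce.

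**Step 1: set the schedule rows side by side (Tables 2 and 8).**

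| Visit | Angiography with radiation | Pregnancy test marked |
|---|---|---|
| Baseline | CTA, MRA or DSA at the physician's discretion (MRA involves no ionising radiation) | Yes |
| Procedure | DSA with 3D | No |
| 6 months | DSA with 3D, and CTA | No |
| 12 months, if Grade 2 or more at 6 months | DSA with 3D; CTA also marked | No |

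Table 5 names the procedure and, separately and in the plural, angiograms. A single test before the implant does not meet that wording for the follow-up studies.

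**Step 2: look for other text that closes the gap.**
- No footnote to Table 2 or Table 8 adds a test, and the text of Section 7.9 does not mention one.
- Exclusion 12 works at entry. Nothing in the supplied text requires contraception to be confirmed again.
- Medical history and medications are marked at Baseline and 12 months only. At 6 months, when implanted subjects are due for imaging, the schedule therefore has no medication review that might show that contraception had stopped.

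**Step 3: age of the last scheduled test.** Visit windows are ±1 month from the implant, and the Baseline test is done on or before the implant date.
- 6-month imaging: 6 − 1 = 5 to 6 + 1 = 7 months after implant, so the test is at least 5 months old.
- 12-month imaging: 12 − 1 = 11 to 12 + 1 = 13 months after implant, so the test is at least 11 months old.

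**Step 4: number of visits, under assumptions.**
- N = 46 subjects with 6-month data (Section 10.6).
- s = share who are pre-menopausal women. The documents do not give it; assumed 0.10 to 0.30.
- g = share at Grade 2 or more at 6 months; assumed 0.30 to 0.70. This brackets two figures in Section 4: complete occlusion in about 30% at 6 months in a randomized coil trial (1 − 0.30 = 0.70) and in 67% at a median of 6 months in a series of 45 WEB patients (1 − 0.67 = 0.33). The planned 70% success rate was not used, because Section 10.6 ties it to a composite outcome.

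Six-month visits = N × s. Twelve-month visits = N × g × s.

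| s | g | 6-month | 12-month | Total |
|---|---|---|---|---|
| 0.10 | 0.30 | 4.6 | 1.4 | 6.0 |
| 0.10 | 0.70 | 4.6 | 3.2 | 7.8 |
| 0.30 | 0.30 | 13.8 | 4.1 | 17.9 |
| 0.30 | 0.70 | 13.8 | 9.7 | 23.5 |

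That is about 5 to 14 six-month visits and 1 to 10 twelve-month visits. These are imaging visits, not pregnancies or exposures, and they include sterile women.

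**The case against.** The strongest reply is that the safeguard is already in the plan. Table 5 is part of the protocol, and Section 12.1.6 requires the PI to "conduct the investigation in compliance with this CIP". The schedule is silent on repeat testing but does not forbid it. Table 5 presents the angiogram as standard of care, and a schedule need not list every routine check before imaging. On this view the point is a missing cross-reference.

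Much of this is fair. Table 5 does bind the site, and usual radiology practice may catch some cases. That sites would skip a test missing from the schedule is an inference. It remains true that the plan makes a promise in one table and omits it from the table that directs the visits.

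Four narrower objections also deserve an answer.
- **CTA.** Table 5 describes the dose of a cerebral angiogram and does not name CTA. Including CTA is an interpretation, though a natural one given the stated concern. It does not affect the finding, because DSA is due at the same visits.
- **Residual risk.** Exclusion 12 does lower it, but only at entry.
- **Visit counts.** The 10% to 30% share has no source in the documents, so the counts indicate scale and do not establish the gap. Only the age of the test follows directly from the plan.
- **Unseen material.** The case report form worksheets are not reproduced and the consent pages were removed. Either may already carry the test, so the finding is limited to Tables 2 and 8.

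**Conclusion.** The concern holds. Tables 2 and 8 do not carry the Table 5 commitment beyond Baseline, and nothing else in the supplied text places a test at the follow-up imaging visits. The firm measure of the gap is the age of the last scheduled test: at least 5 months at the 6-month DSA and CTA, and at least 11 months at the 12-month imaging. The estimate of 6 to 23 affected visits depends on the two assumed ranges.

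The Procedure column is also unmarked although Table 5 names the procedure, so the Baseline test covers the implant only if it is done close to that day.

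This should be corrected, because it concerns subject safety and is cheap to put right. It has no bearing on the statistical conclusions.

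**What to change.** 1. In the pregnancy-test row of Tables 2 and 8, keep the Baseline mark and add marks for pre-menopausal women at 6 months and, if imaged, at 12 months.
2. Add a footnote to that row: urine or blood test, with the result available before any follow-up DSA or CTA; if the Baseline test was not done shortly before the implant, repeat it before the procedure. The footnote should exempt baseline imaging done before enrollment, since the tables allow this: "Baseline image screening can be completed within 3 months prior to enrollment".
3. Reword Table 5 so that it calls for a test before the procedure and before each follow-up DSA or CTA. This makes the timing firmer and names CTA, so it slightly strengthens the present text as well as aligning it.

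The cost is two marks and one footnote in each of two tables and one wording change in Table 5. Under the assumptions above it means about 6 to 23 urine or blood tests at follow-up. Since DSA is due at the same visits as CTA, naming CTA adds no visits to those Table 5 already covers. A repeat before the procedure would be extra, but Table 5 already names the procedure.
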